7.4 Prior and concomitant treatment

The type (brand name and active ingredient) and duration of administration of all medications taken at the time of the inclusion or during the study will be recorded on the Case Report Form (CRF). Dosage, route of administration, and indication will also be specified.

7.5 Prohibited treatments

The use of concomitant chemotherapy, radiotherapy, biological therapy (including cytokines, however erythropoietin is allowed), and steroid therapy (inhaled, oral or topical steroids for treating mild to moderate asthma, allergies or ocular inflammations, typically at ≤ 500 ug/day of fluticasone or equivalent are allowed), is prohibited as long as the patient is on the study and must have been stopped at least 2 weeks prior to first dose administration. Radiation for palliation of pain is acceptable. Participation in any clinical study involving any medications or treatments, whether approved or investigational, is prohibited.

8 Correlative studies-

To assess nivolumab correlative biologic studies to assess immunomonitoring of lymphocytes subsets including T and NK cells and ex-vivo assessment of immune functional activities. If possible, similar studies will be conducted on the bone marrow aspirates as well.

8.1 Instructions for subsites handling correlative samples

Subsites are requested to procure correlative samples at specified time points. Peripheral blood mononuclear cells (PBMC) and bone marrow samples are to be ficolled and cryopreserved in freezing media aliquots with subject number and cycle/day of collection marked. These may be batched shipped quarterly, Monday - Thursday. The address to which to send samples is:

[name] Laboratory
[name]
[name]

8.2 Correlative laboratory investigations

We will conduct extensive immunomonitoring of T and NK cell subsets at baseline and upon completion of each 28-d cycle of therapy. We will focus our analyses principally on the absolute and relative percentage of CD8(+) T cells and CD4(+) T cell subsets including: CD4(+)C45RO(+)CD62L(-)CCR7(-) effector/memory T cells, CD4(+)CD62L(-)CD127(+) peripheral memory T cells, and CD4(+)CD25^{bright}FOXP3(+),CD127^{low/absent} regulatory T cells. We will study Th1/Th2/Th17 polarization in T cells (by expression of CD3, CD4, CD193, CD293, CXCR3, CCR4, and CD45).

8.3 T-cell specific correlative science

Immunologic assessments will be performed prior to each cycle of therapy, and at 1, 3, and 6 months following the last cycle of therapy. At each time point, PBMC will be isolated from peripheral blood by ficoll density centrifugation and cryopreserved. Following completion of the study, PBMC will be thawed and 1×10^6 PBMC will be cultured with lysate generated by freeze thaw cycle of 1×10^5 unselected MM cells. As a control, PBMC will be cultured with tetanus toxoid (10 ug/ml) or media alone. Following 5 days of coculture, expression of IFN- γ by CD4(+) and CD8(+) populations will be determined by intracellular FACS analysis. Cells will be restimulated with tumor lysate for 6 h and cultured overnight with 1 ug/ml GolgiStop. The cells will be stained with CD4 or CD8 antibodies conjugated to FITC and permeabilized with Cytofix/Cytoperm plusTM. Cells will be stained with PE-conjugated anti-human IFN- γ , fixed in 2% paraformaldehyde and analyzed by flow cytometry. The effect of therapy on levels of circulating tumor reactive T cells will be determined by quantifying IFN- γ expressing CD4(+) and

CD8(+) T cells. The impact of nivolumab and Len on tumor reactive T cells will be determined by comparing the pre-treatment levels with the peak level observed following therapy. The cytolytic capacity of tumor reactive lymphocytes will be determined by measuring expression of granzyme B and perforin in CD8(+) T cells following *ex vivo* exposure to autologous tumor lysate. The presence of naïve, memory effector, and central memory cells in the tumor reactive population will be determined by multichannel FACS analysis. The percentage of activated effector cells will be elucidated by quantifying the percentage of CD4(+)CD25(+) CD69(+) cells. Tregs will be quantified by assessing expression of FOXP3 for the CD4(+)CD25(+)CD127^{low/absent} population. When cell yields allow, we will assess the capacity of T cells to lyse autologous tumor cells in a standard chromium release assay. We will also examine the effect of nivolumab and Len on immunologic responses against previously identified tumor antigens. XBP-1, OFD-1, SOX2, MUC1, and CD138 have been identified as MM associated antigens. In HLA-A2.1 patients, we will quantify the number of CD8(+) T cells binding tetramer constructed from these antigens (as cell yields allow) at serial time points in the circulation. The persistence of tetramer(+) cells in the circulation will be determined. Functional characteristics of the tetramer positive population will be determined by measuring IFN- γ , granzyme B, IL-4, and IL-10 expression in the tetramer(+) cells by intracellular FACS staining.

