1 BACKGROUND AND RATIONALE

1.1 Multiple Myeloma

Multiple myeloma (MM) is the second most common hematological malignancy with approximately 22,000 new cases diagnosed each year in the United States. MM is associated with profound and widespread disarray of both the adaptive and innate arms of the immune system¹ specifically including: loss of effector T cell function^{2,3}, defective maturation and function of antigen presenting cells,^{4,5} increased levels of regulatory T cells (Treg),⁶ humoral immune deficiency, as well as natural killer (NK) cell immunity.^{7,8} This immunosuppressive milieu, in turn, is crucial to promoting disease progression as both T cell⁸ and NK cell⁹ mediated tumor-specific immune responses have been demonstrated in early MM; however, these effects are lost in the inexorable progression of the disease.^{9,10} Moreover, most standard treatment options (including chemotherapy, radiation, and high-dose corticosteroids) offer only modest benefit, and also contribute to further immune suppression. Due to both disease-related and treatment-related immune compromise, infection remains the most common cause of death for pts with MM.¹¹ Until recently, little has been known regarding the mechanisms by which immune dysfunction and immuno-evasion occur.

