6.9.4 Sample collection for immunologic correlative studies

All patients enrolled on this trial will have samples procured for all proposed laboratory correlative studies as summarized below. With each cycle, approximately 30-mL of blood will be collected and sent to [name]'s lab for processing. Upon receipt, each sample will be recorded and coded with a unique sample number to keep patient identification confidential. PBMCs and plasma (and/or serum) will be aliquoted and cryopreserved. The vials of viably frozen cells for all time points for each patient will be thawed at the same time whenever possible to avoid inter-experimental variability.

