6.9.5 Schedule for correlative studies

Laboratory correlative studies will be obtained at screening, days 1 and 15 of the cycles and off study. Off-study correlates should be obtained at the time the patient is removed from protocol for any reason. In addition, continued T-cell correlate will be done at 1, 3, and 6 months after removal from study. Specimens obtained include BM aspirate (10-15 ml in green-top tubes using heparinized syringe) and peripheral blood (Three-10 ml green top tubes, 2 for cells and 1 for plasma).

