- h. Baseline and periodic ECGs should be performed during treatment as indicated in the flow chart. In patients who have ECG abnormalities, ECGs should be performed more routinely as clinically indicated. ECGs post-baseline should be performed as indicated
- i. Myeloma monoclonal protein assessments (Serum protein electrophoresis & immunofixation, immunoglobulin levels, serum free light chain assay) will be performed on day 1 of each cycle as well as off study.
- j. 24hr urine monoclonal protein assessment (Urine protein electrophoresis & immunofixation) will be performed at screening and as required for response assessment.
- k. Unilateral bone marrow (BM) biopsy will be done at baseline and at end of 4th cycle and evidence of progression for patients with non-secretory multiple myeloma
- l. Lenalidomide must be prescribed through and in compliance with Celgene's RevAssist® program. Prescriptions must be filled within 7 days. Any unused lenalidomide should be returned to the patient for disposition in accordance with the RevAssist® program.
- m. Dexamethasone will be started on cycle 3 only if stable disease after 2 cycles.
- n. Lenalidomide and dexamethasone will start on day 1 of each cycle. Patients will do not need to be in clinic to initiate this as all patients would have been exposed to both. Lenalidomide will be ordered for the next cycle. A pregnancy test (urine or B-HCG) will also be ordered at this time and must be negative prior to starting treatment.
- o. Laboratory correlative studies will be obtained. This will be collected through C5D1, at the off study visit, and at 1, 3, and 6 months post off-study. Off-study correlates should be obtained at the time the patient is removed from protocol for any reason.
- p. Vital signs (temperature, blood pressure, pulse rate, respiratory rate) and ECG will be closely monitored prior to, during, and after first drug infusion to avoid general infusion-related reactions. Routine vital signs with subsequent infusions, unless indicated otherwise.
- q. Correlative studies for the bone marrow aspirate will be done at screening, cycle 5 day 1, and at the off study visit.

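### Section 8.3 measures the drug effect on tumor-reactive T cells as pre-treatment against the peak of several later samples, which under stable but variable levels shows a rise without any drug effect

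*Combined protocol and SAP*

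**What the plan says.** For IFN-gamma-expressing CD4(+) and CD8(+) T cells, Section 8.3 states how the effect of the two drugs is to be judged: by "comparing the pre-treatment levels with the peak level observed following therapy". It does not define which samples the peak is taken over, and the documents give more than one schedule:

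- Section 8.3: "Immunologic assessments will be performed prior to each cycle of therapy, and at 1, 3, and 6 months following the last cycle of therapy".
- Section 6.9.6, footnote o: "This will be collected through C5D1, at the off study visit, and at 1, 3, and 6 months post off-study".
- Section 6.9.5 lists screening, days 1 and 15 of the cycles and the off-study time, and adds "continued T-cell correlate will be done at 1, 3, and 6 months after removal from study".

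Two provisions bear on measurement noise. Section 8.3 says "As a control, PBMC will be cultured with tetanus toxoid" or with media alone, but gives no rule for using these cultures to adjust a peak. Section 6.9.4 says a patient's vials "will be thawed at the same time whenever possible to avoid inter-experimental variability". Section 7.1.1 adds that marker changes will be plotted and summarised quantitatively, and calls the correlative analyses no more than exploratory. The T-cell subset, NK-cell and monocyte analyses in Sections 8.2, 8.4 and 8.5 do not use a peak.

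**The concern.** Each patient's post-treatment value is a maximum over several noisy measurements, while the pre-treatment value is a single draw by the calendar. The maximum is at least as large as the value at any one later time, so the difference leans upward even when nothing has changed. With a single arm (Section 5.1) there is no comparison group in which the same lean could be seen and subtracted, and a larger sample would not remove it.

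What is at stake is the reading of this one assay. Section 7.1.1 expects the correlative work to inform mechanism and to supply preliminary data for later studies. A pre-treatment versus peak summary could be read as immune activation when it reflects only sampling variation. The primary endpoint and the trial's decision rule are not affected.

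**Working it through.** The plan gives no SD, power or expected change for this comparison, so there is no figure to reproduce.

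**Inputs.** There are 18 patients (Section 5.4) and one pre-treatment sample (C1D1, calendar). The number of later samples, k, depends on the reading:

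- k = 3: only the 1-, 3- and 6-month draws.
- k = 4: C2D1 to C5D1. The stop at C5D1 comes from footnote o, not from Section 8.3.
- k = 7: both sets.
- k = 14: Section 8.3 read alone over 12 cycles, that is 11 pre-cycle draws (cycles 2 to 12) plus 3 follow-up draws.

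The off-study and day-15 draws are not counted. Adding the off-study draw to k = 7 gives k = 8; adding the day-15 draws of cycles 1 to 4 as well gives k = 12.

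**Null model (assumed).** Each patient's values vary around an unchanged mean with within-patient SD s. With independent normal values:

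- expected (peak - pre-treatment) = s × E[maximum of k standard normals]; for k = 3 this is 3/(2√π) = 0.846;
- P(peak > pre-treatment) = k/(k+1), for any continuous distribution.

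| k | Rise, independent | Patients rising | Rise, correlation 0.8 per cycle | Patients rising |
|---|---|---|---|---|
| 3 | +0.85 s | 3/4 = 75% | +0.61 s | 69% |
| 4 | +1.03 s | 4/5 = 80% | +0.55 s | 75% |
| 7 | +1.35 s | 7/8 = 87.5% | +0.98 s | 85% |
| 14 | +1.70 s | 14/15 = 93% | not computed | not computed |

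The correlated columns are simulations on calendar spacing: 28-day cycles, last cycle 5, follow-up draws at 1, 3 and 6 months. There k = 3 exceeds k = 4 because the follow-up draws lie further apart and are less correlated. Of 18 patients, 18 × 0.80 = 14.4 would appear to rise at k = 4 and 18 × 0.875 = 15.75 at k = 7, under independence. A fixed time point gives 50% and a mean change of zero.

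**A second baseline.** If a screening sample were averaged with C1D1, the expected rise would not change (0.85, 1.03 and 1.35 s), because averaging alters the baseline's variance and not its mean.

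**Scale.** The within-patient CV is not given. If it were 20% to 50% (assumed range, lognormal, independent values), the null peak-to-baseline ratio would be about 1.2 to 1.6 at k = 4 and 1.3 to 1.9 at k = 7.

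**Relaxing stationarity.** Section 1.1 says of tumor-specific immune responses that "these effects are lost in the inexorable progression of the disease", so a late decline is plausible. With the three late levels lowered by 1 s:

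- k = 3: -0.16 s under independence (simulated -0.155; by formula 0.846 - 1 = -0.154) and -0.39 s at correlation 0.8, with 45% and 37% of patients rising. No apparent rise is left.
- k = 7: +1.09 s and +0.65 s, with 82% and 78% rising, because the C2D1 to C5D1 draws still feed the peak.

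**The case against.** The strongest reply is that this is declared exploratory work, that Section 7.1.1's plots and quantitative summaries may show the whole time course, and that whether a patient ever mounted a response is a fair descriptive question. Much of that stands, and it is why the point is minor. It does not answer the point itself: Section 8.3 still names the peak comparison as what determines the drugs' impact, and nothing in Section 7.1.1 corrects it. Joint thawing lowers s, and with it the size of the lean, but leaves biological variation in place.

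Three stronger readings are tempting, and the documents do not support them:

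- A reader might infer that the summary will suggest activation whatever happens. It need not: if the peak is taken over the follow-up draws only and late levels fall by 1 SD, the apparent rise vanishes. The documents do not settle which draws count.
- A reader might infer a near-certain false positive. A paired t-test at two-sided 5% with 18 patients would indeed reject in 77%, 92% and 99.6% of null trials for k = 3, 4 and 7 under independence, but the plan names no test for this comparison.
- A reader might infer a spurious link with response, since patients who leave early supply fewer draws and so a lower expected peak. Section 7.1.1 does contrast responders with non-responders, but does not say that the peak will be the change used.

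**Conclusion.** The concern holds in conditional form and is minor. With stable within-patient levels and no drug effect, the Section 8.3 comparison is positive on average: +0.85 to +1.35 SD for 3 to 7 later samples under independence, +0.55 to +0.98 SD at correlation 0.8 per cycle on calendar spacing, and +1.70 SD if Section 8.3's own schedule runs to 12 cycles (independence). The direction follows from taking a maximum under stationarity. The size rests on the assumed normal model, the correlation, the sample count and a within-patient SD that the documents do not give. A late decline cancels the apparent rise only if the on-treatment draws are excluded. The reach is one exploratory assay, with no test, threshold or trial decision attached.

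**What to change.** Replace the peak sentence in Section 8.3 with wording such as:

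> The effect of treatment on tumor-reactive T cells will be summarised as the mean within-patient paired change in IFN-gamma-expressing CD4(+) and CD8(+) T cells from the pre-treatment sample to C5D1 (lead time point), with a 95% confidence interval. Changes to C3D1 and to the 1-, 3- and 6-month follow-up draws will be summarised in the same way as supporting description. The number of patients contributing will be given at each time point. The peak will be reported as description only, with the number of post-baseline samples per patient.

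Naming a lead time matters. Five times by two cell populations make ten intervals, and in a null simulation with CD4 and CD8 taken as independent, 31% to 34% of trials had at least one interval excluding zero. With C5D1 as lead there are two intervals, and under the same independence the chance is 1 - 0.95² = 9.75%. C5D1 follows four cycles, which matches the primary response assessment.

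Two details need settling alongside:

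- State one anchor for the follow-up draws. Section 8.3 counts from the last cycle; Sections 6.9.5 and 6.9.6 count from removal from study.
- Footnote m says "Dexamethasone will be started on cycle 3 only if stable disease after 2 cycles". C3D1 is therefore free of added dexamethasone only if drawn before cycle 3 dosing. Section 8.3's pre-cycle timing requires that, but the calendar's ±4-day window does not guarantee it.

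The cost is wording only: the draws are already scheduled, and Section 8.3 runs the assays after the study is complete. There are downsides. A transient rise between the chosen times would show only in the descriptive peak. C5D1 includes patients given dexamethasone. Patients who leave early do not contribute to later changes. Precision is modest: the C5D1 interval is about ±0.5 to 0.7 SD with 18 patients and ±0.8 to 1.1 SD with 9, for correlations from 0.8 down to 0.

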8.4 NK-cell specific correlative science

We will quantitate CD56^{bright} and CD56^{dim} NK cell subsets in PBMC and other markers of NK cell maturity (proportion of NK cells expressing CD16 and CD117) and developing intermediates in peripheral blood. We will also perform immunophenotyping of NK cell subsets for expression of trafficking antigens (in particular CXCR4 which we have shown to be modulated by nivolumab on NK cells) and markers of activation (CD158, CD69) and degranulation (LAMP-1, LAMP-3, CD107a, CD107b, CD159, and CD314) which may be influenced by nivolumab and Len. Notably, our group has optimized an “immunome” flow cytometry-based profiling technique to allow these characterizations from a very modest amount of pt PBMC to minimize volume of blood collected for correlative science studies. Finally, we will perform *ex vivo* functional assays against MM cell line targets and purified, autologous MM tumor samples obtained at baseline and after each cycle of therapy including trafficking, immune complex and cytotoxicity assays as described by our group previously.⁴⁴ We will also attempt to verify our preclinical finding regarding down modulation of PD-L1 on MM tumor cells by Len by comparing PD-L1 expression on pt MM tumor cells at baseline and after one cycle of therapy. We will purify CD138 (+) MM cells from bone marrow aspirates of pts obtained at baseline and after 4 cycles of treatment and assess PD-L1 expression by flow cytometry.

8.5 CD14(+) monocyte specific, correlative science

We will evaluate the expression of PD-L1 and PD-L2 on CD14 (+) monocytes at baseline and after treatment with nivolumab after each cycle of therapy. We will specifically study the induction of these antigens on CD14 (+) cells as a consequence of nivolumab administration. We will attempt to correlate the expression PD-L1 on CD14 (+) cells with clinical activity determined by response rate and progression-free survival if allowable by sample size power. Otherwise, we will limit these analyses to hypothesis-generating, descriptive evaluation.

9 Investigational drugs

9.1 Nivolumab

Nivolumab (humanized monoclonal antibody) for parenteral administration is supplied as a 10 mg/mL clear solution and is preservative-free. Each vial consists of 100 mg in 10 ml solutions.

Label of the Drug: The container label and the immediate outer carton label of the investigational product to be used in the clinical study will contain the following information: product name and strength, lot number, protocol number, vial number, manufacturer's name and address, recommended storage conditions, and an investigational caution statement.

Storage of the Drug: Vials of nivolumab injection must be stored at 2°C to 8°C (36°F to 46°F) and protected from light and freezing.

Preparation of Nivolumab for Administration: The solution will be prepared by a pharmacist, the Investigator, or a study nurse. Appropriate aseptic techniques should be used. Each vial contains **approximately** 100 mg/10 ml nivolumab. The bag will be identified with the patient number. Parenteral solutions should be inspected visually for particulates and discoloration prior to administration. Once the infusion is prepared, it should be administered within 24 hours. If Not used immediately, the infusion solution may be stored under refrigeration conditions (2°C to 8°C, 36°F to 46°F) for up to 24 hours, and a maximum of 8 hours of the total 24 hours can be at room temperature (20°C to 25°C, 68°F to 77°F) and room light. The maximum 8-hour period under room temperature and room light conditions includes the product administration period.

Method of Administration: nivolumab will be administered intravenously on day 1 and 15 of each 28 day cycle. The drug is diluted into a 250mL saline bag and will be administered over one-hour. In the event that Grade 3 or higher toxicity occurs during infusion, administration of nivolumab should be stopped immediately. Administration of nivolumab could be resumed only after the toxicity has resolved using the slowest rate of infusion (50mL/hr). Vital signs will be measured prior to infusion and every 15 minutes for the first hour, then every 30 minutes for an additional hour, and then once an hour until the end of infusion. The window for vital signs will be per institutional standard of practice.

9.2 LENALIDOMIDE (Revlimid™)

Lenalidomide (REVLIMID®), a thalidomide analogue, is an immunomodulatory agent with anti-angiogenic properties. The chemical name is 3-(4-amino-1-oxo 1, 3-dihydro -2H-isoindol-2-yl) piperidine-2, 6-dione. Lenalidomide has been studied extensively in myeloma and it is approved for use in newly diagnosed and in relapsed MM.

Supply: REVIMID® (lenalidomide) is available in 5, 10, 15 and 25 mg capsules for oral administration. Each capsule contains lenalidomide as the active ingredient and the following inactive ingredients: lactose anhydrous, microcrystalline cellulose, croscarmellose sodium, and magnesium stearate. The 5 mg capsule shell contains gelatin, titanium dioxide and black ink. The 10 mg capsule shell contains gelatin, FD&C blue #2, yellow iron oxide, titanium dioxide and black ink.

Elimination: The metabolic profile of lenalidomide in humans has not been studied. In healthy volunteers, approximately two-thirds of lenalidomide is eliminated unchanged through urinary excretion. The process exceeds the glomerular filtration rate and therefore is partially or entirely active. Half-life of elimination is approximately 3 hours.

Pregnancy: Due to its structural similarities to thalidomide, a known human teratogen, lenalidomide is contraindicated in pregnant women and women capable of becoming pregnant. When there is no alternative, females of childbearing potential may be treated with lenalidomide provided adequate precautions are taken to avoid pregnancy. Females must commit either to abstain continuously from heterosexual sexual intercourse or to use two methods of reliable birth control, including at least one

highly effective method (e.g., IUD, hormonal contraception, tubal ligation, or partner's vasectomy) and one additional effective method (e.g., latex condom, diaphragm, or cervical cap), beginning 4 weeks prior to initiating treatment with REVCLIMID® (lenalidomide), during therapy with REVCLIMID® (lenalidomide), during therapy delay, and continuing for 4 weeks following discontinuation of REVCLIMID® (lenalidomide) therapy. If hormonal or IUD contraception is medically contraindicated, two other effective or highly effective methods may be used.

Deep Venous Thrombosis and Pulmonary Embolism: This drug has demonstrated a significantly increased risk of DVT and PE in patients with multiple myeloma who were treated with REVCLIMID® (lenalidomide) combination therapy. Patients and physicians are advised to be observant for the signs and symptoms of thromboembolism. Patients should be instructed to seek medical care if they develop symptoms such as shortness of breath, chest pain, or arm or leg swelling. Prophylactic anticoagulation or antiplatelet therapy prescribed in conjunction with REVCLIMID® (lenalidomide) is required for patients enrolled in this current trial.

